FAsTask Video Code. The FAsTask is an interactive family problem solving task that will be used to provide an in-vivo assessment of parenting behaviors. We have limited the assessment to three tasks that align with our primary aims: 1) Limit Setting (parent leads a 5 min discussion about a time they had to set a limit); 2) Substance Use Norms (parent leads a 5 min discussion on family views about substance use); and 3) Monitoring and Listening (teen leads a 5 min discussion on their peers and parent listens and reacts). Co-I [name] has created a structured clinical codebook that defines each item to be coded and gives specific examples of high and low-scoring observations. Interactions will be observed during each phone or video conference assessment and will be audio recorded. Tapes will be coded by raters blind to condition: 20% of tapes will be double coded.

Data Analysis Plan.

All 60 parents will be included in statistical analyses consistent with an intent-to-treat (ITT) model. Prior to the main analyses, we will run descriptive statistics on key variables to examine distributional properties, identify outliers, and transform variables as needed. The two treatment conditions will be compared on all baseline demographic and clinical variables. Pre-existing differences on any variables and any additional treatment received will be controlled in subsequent analyses.

Missing data. GAIN data is entered into the GAIN's proprietary software, which offers instant error checks and validation reports to prevent missing data. Other forms will be entered directly into study laptops using REDCap (Research Electronic Data Capture), a secure web-based application, to reduce missing data and entry errors. Attrition analyses will compare follow-up completers and non-completers on baseline clinical and demographic variables to determine if they differ systematically. If necessary, we will use standard methods of multiple imputation [123] for variables where unplanned missingness is an issue. For each follow-up time point, we will conduct analyses to identify systematic biases that may have arisen due to non-random dropout.

Aim 1. In the RCT, feasibility will be examined via enrollment rates ($\geq 80\%$) and indicators of engagement, with these preliminary targets: attendance of ≥ 3 of 4 coaching sessions pre-

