We will begin by comparing the DV scores (means of continuous DVs and percentages of categorical DVs) at each assessment. We will conduct separate mixed models predicting each DV by condition, controlling for the following covariates: baseline status on the DV, baseline differences between groups, and any mental health or substance use treatment received over the follow-up period. We will analyze the effect of PW dosage on each DV and calculate partial eta squared (η^2) to estimate the proportion of variance caused by PW. We are underpowered to test mediation, but will examine the effects of PW on our putative mediators (Aim 4), and correlations between change in the mediators and change in the primary outcomes (Aims 2-3), with the goal of finding promising trends to pursue in a larger trial. We will cautiously attempt more sophisticated analyses using hierarchical modeling, a flexible approach to analyzing change that has been frequently used by the PI [37, 90, 91]. Mixed models are ideally suited to address Aims 2-4, by enabling us to compare the conditions at each time point while accounting for the correlation of observations over time. Although convergence is challenged in a small sample, it is feasible. Our primary goal will be to provide measures of association and 95% confidence intervals to reveal the ES of PW on each DV.

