Sample Size, Power, and R01. We chose to recruit 60 subjects for the RCT conservatively estimating that 15-20% may be lost to follow-up, leaving 50 subjects with complete parent-teen data. This number will allow us to make judgments regarding feasibility and acceptability. As noted in Preliminary Studies, ES estimates in prior PW studies have ranged from small to very large; the only ASUD study found small to medium ES, but unlike this application, that study did not offer in-person support or an online parent board. We therefore may find ES in the medium range. Despite issues with ES stability in small samples [124], a small to medium ES paired with high levels of feasibility and acceptability would be an indication that the adapted PW intervention should be tested in a larger trial. Based on the detected ES, post-hoc power analyses will be conducted to determine the number of parents required for a fully powered RCT. For instance, for power of .8, a small ES ($d = .3$) would require a sample of 175 per group, while a medium ES ($d = .5$) would require a much smaller sample of 64 per group. If our results are promising, we will develop a fully powered R01 application in Months 31-36 (see Table 2) to evaluate the adapted PW under ecologically valid conditions. To speed the translation of research findings to practice, our R01 will use a hybrid effectiveness-implementation design to simultaneously test the effectiveness of the intervention and inform the ideal implementation strategy [125].

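### Aims 2-4 covariates are chosen from observed baseline differences with no threshold or list, so the effect size depends on how the rule is read and, for continuous outcomes, the CI is generally wider

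*Combined protocol and SAP*

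**What the plan says.** The opening of the Data Analysis Plan states: "The two treatment conditions will be compared on all baseline demographic and clinical variables". It continues: "Pre-existing differences on any variables and any additional treatment received will be controlled in subsequent analyses". The Aims 2-4 paragraph carries this into the models: each mixed model includes "baseline status on the DV, baseline differences between groups", followed by treatment received over follow-up.

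Neither place gives a significance level, a standardised-difference cut-off or a list of candidates. The only baseline covariate fixed in advance is the baseline value of the outcome. The three urn factors in the Randomization paragraph (sex, race/ethnicity, days of use) are not named as covariates, and neither is site. Under Biological markers, urine screens are taken only at follow-up, so they have no baseline value to adjust for.

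For these aims the plan says: "Our primary goal will be to provide measures of association and 95% confidence intervals". Sample Size, Power, and R01 then says: "Based on the detected ES, post-hoc power analyses will be conducted to determine the number of parents required". It adds that d = 0.3 "would require a sample of 175 per group", against 64 per group at d = 0.5.

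**The concern.** In a randomised comparison, baseline differences arise by chance. Picking covariates by the size of that difference ignores whether they predict the outcome. It favours variables correlated with arm, which inflates the variance of the treatment effect, and it can leave out prognostic variables that happen to be balanced. With no threshold stated, the model is not settled until the data are seen, and two competent analysts can fit different models to the same outcome.

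What is at stake is the effect size and 95% CI for each outcome, which are the stated product of the Aims 2-4 analysis.

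**Working it through.** **1. The plan's own figures.** With n per group = 2(1.96 + 0.842)²/d² = 15.70/d², d = 0.3 gives 174.5, so 175. d = 0.5 gives 62.8, so 63, or 64 by the noncentral t. The stated 175 and 64 are reproduced, taking alpha as two-sided 0.05 (not stated). Attrition: 60 × 0.85 = 51 and 60 × 0.80 = 48, which bracket the stated 50.

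**2. Candidate pool.** The plan gives no count. A tally from the Measures section is: demographics 5, treatment history 2, use days 3, SFS 1, sexual behaviour 4, school days 3, legal days 2, PMQ 2, PACS 4, FAsTask 3 (one score per task assumed). The total is 29, or 30 with site. A low case of 10 was also run. Expected chance selections among independent candidates are 0.5 (5% rule) and 2.0 (20% rule) with 10, and 1.5 and 6.0 with 30. The chance of at least one at 5% is 1 - 0.95^10 = 40% or 1 - 0.95^30 = 79%.

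**3. Simulation (all settings assumed).** 60 dyads were allocated by an urn on three binary factors and 50 were analysed at random. The outcome was continuous, the true effect 0.4 SD, and the baseline outcome was always in the model. R² is the share of residual variance explained jointly by the fixed set (three urn factors and site). There were 2,000-3,000 runs per setting.

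**4. Dependence on the reading.** The p<0.05 and p<0.20 readings of the same data gave estimates 0.10 SD or more apart in about 14-21% of trials with 10 candidates. With 30 it was 33-34% when the other candidates were correlated 0.3, and 42-46% when all were independent.

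**5. Mean 95% CI half-width (SD units).** Repeat runs agreed within about 0.003.

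| Candidates | R² | 5% rule | 20% rule | Fixed set |
|---|---|---|---|---|
| 10 | 0 | 0.586 | 0.604 | 0.594 |
| 10 | 0.10 | 0.585 | 0.600 | 0.563 |
| 10 | 0.20 | 0.584 | 0.597 | 0.531 |
| 30 | 0 | 0.617 | 0.681 | 0.595 |
| 30 | 0.10 | 0.615 | 0.675 | 0.563 |
| 30 | 0.20 | 0.613 | 0.671 | 0.529 |

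Baseline outcome alone gives about 0.575, narrower than either selection rule in every setting. For the average over three visits (ICC 0.5, 10 candidates), the 5% rule, 20% rule and fixed set give 0.475, 0.490 and 0.482 at R² = 0, and 0.477, 0.489 and 0.446 at R² = 0.10.

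**6. Analytic check.** Half-width with four added terms = 1.96 × √(4/50) × √[(47/43)(1 - R²)]. Without them it is 1.96 × 0.2828 = 0.554. With them it is 0.580 at R² = 0, 0.550 at 0.10 and 0.518 at 0.20. Break-even is R² = 1 - 43/47 = 0.085. These values are a little below the simulated ones because the formula uses a normal quantile and ignores chance correlation of covariates with arm.

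**7. Validity and sampling error.** Mean estimates were about 0.38-0.41 under every model. Coverage was 94-97% under the rule and 94-96% with the fixed set. The SD of the fixed-set estimate was 0.26-0.30, so the chance of missing the truth by more than 0.10 is P(|Z| > 0.10/0.26) = 70% to P(|Z| > 0.10/0.30) = 74%.

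**8. Categorical outcomes.** A logistic run with n = 50 compared four added terms (log-OR 0.6 each) with none. The log-OR half-width rose from 1.24 to 1.47 and the mean log-OR moved from -0.70 to -0.85. The SD of the standardised risk difference was 0.137 with the terms and 0.134 without. Non-convergence was 0.2% at a control risk near 50%, but 26% near 15% (9% without the terms).

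**The case against.** The strongest reply is that this is a pilot. Aims 2-4 are secondary, n = 60 is justified by feasibility and acceptability, and the sample-size section itself concedes that effect sizes are unstable in small samples. That stands, and it limits the consequence.

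Several stronger readings are tempting, and the documents do not support them:

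- *The rule would mis-size the next trial.* From d = 0.4 (15.70/0.16 = 98.1, so 99 per group), a shift of 0.10 leads to the plan's 64 or 175. But sampling error alone exceeds 0.10 SD in about 70% of trials, so a fixed set would not make that sizing reliable either.
- *The rule biases the effect or invalidates the CI.* Neither was visible. The simulations leave out adjustment for treatment received in follow-up (a separate issue), non-random dropout and non-normal outcomes.
- *The urn factors will be left out.* That holds only for p-value readings: at least one is selected in about 1% of runs at 5% and 15-17% at 20%. A standardised difference above 0.25 selects one in 42-46%.
- *A fixed set is always narrower.* It is not. With 10 candidates and R² = 0 it is slightly wider than a 5% rule, and the documents give no prognostic strength to settle where this trial lies.

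It could also be said that the rule may catch strong predictors that a fixed set omits. With 30 candidates, the other 26 carrying R² = 0.20-0.40 and the fixed set none, the fixed set was still narrower (0.594 against 0.610-0.611 for the 5% rule).

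Finally, it is unclear that site varies in this trial. Section B and Study Purpose speak of one new site, while section B also lists two programmes and the eligibility section refers to both facilities.

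**Conclusion.** The point holds as a correctable weakness in the analysis rule. The plan states a selection rule that leaves the model to the analyst. At R² = 0.10 the continuous-outcome CI is wider than with the fixed set by about 4% (0.585/0.563) to 7% (0.600/0.563) with 10 candidates, and by 9% (0.615/0.563) to 20% (0.675/0.563) with 30. Against baseline outcome alone the excess runs from 2% (0.585/0.575) to 17% (0.675/0.575).

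The advantage over selection does not depend on the urn factors being prognostic, since the baseline outcome alone already beats both rules. The advantage of the four added terms over baseline alone does: it needs R² above about 0.085. All sizes rest on the assumed candidate counts, thresholds and prognostic strength, on random dropout and on 1:1 allocation. The harm is avoidable discretion and some lost precision in secondary pilot analyses. It is not a threat to validity.

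**What to change.** In the Aims 2-4 paragraph and in the opening of the Data Analysis Plan, replace adjustment for observed baseline differences with a prespecified set. Report the baseline table descriptively, without selection.

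- **Continuous outcomes:** baseline outcome plus the three urn factors. Enter days of use as a continuous variable, defined as for the urn and omitted where it duplicates the baseline outcome. State that definition, because the Measures section analyses alcohol, marijuana and other drugs separately. Add site if both facilities contribute randomised dyads, and reconcile the passages on one site or two.
- **Outcomes without a baseline value** (urine screens, and also relapse and latency to first use): name the urn days-of-use variable as the substitute.
- **Categorical outcomes:** the plan reports "means of continuous DVs and percentages of categorical DVs" and says of its models: "Although convergence is challenged in a small sample, it is feasible". Prespecify only the baseline term or its substitute, plus site if applicable, falling back to the baseline term alone on non-convergence. Report a marginal risk difference with its 95% CI. No precision gain is claimed here, and this reduced set was not itself simulated against the selection rule.

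The cost is wording only, with no new data. The downside is up to four model degrees of freedom, and a slightly wider CI if the factors are not prognostic (0.594 against 0.586 for a 5% rule with 10 candidates, or about 0.575 for baseline outcome alone).

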- 2a: indicators of substance use: substance use frequency, severity of substance use symptoms, rates of relapse, and biological markers (i.e., urine drug screens).
- 3a: high-risk behaviors commonly related to substance use: externalizing behavior, sexual risk behavior, school truancy, and criminal behavior.
- 4a: parenting behaviors: parental monitoring and communication, as demonstrated by both parent and adolescent report and observed during an in vivo task.

2. Detailed Study Methodology

STUDY PURPOSE. We are seeking approval to conduct a randomized control trial of 60 parents whose adolescents are preparing for discharge from residential substance use treatment at a new remote site. The goals of this project are to: (1) examine if the adapted intervention and the study assessment procedures are feasible and acceptable to study participants; (2) evaluate the preliminary effectiveness of the adapted intervention.

STUDY POPULATION. We are currently seeking approval to enroll 60 parent-adolescent dyads (i.e., a total of 12- participants) for a randomized trial.

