Retention procedures. At baseline, multiple sources of contact information will be recorded for parents and ASUD to prevent attrition. A demographic form will be administered aloud by a research staff member at Brown via Zoom and information will be obtained and stored in hard copy form in locked filing cabinets in the PI's office at Brown University. Contact information will be updated by periodic phone calls and during assessments. Reminders will be made via phone and mail. The PI will hold weekly case review meetings to review no-shows and outreach attempts, and discuss plans to complete contact with missing participants. Compensation for completion of questionnaires and interviews/discussions escalates slightly from \$40 at baseline, 6 and 12 weeks to \$60 at 24 week followThis compensation schedules recognizes the increased effort associated with scheduling a follow-up and providing a urine screen after the teen has been discharged. We have used these retention procedures (e.g., reminder calls, periodic update calls, escalating compensation) with success in current and prior projects.

Randomization. In the randomized pilot trial, parent-adolescent dyads will be randomized to the adapted PW condition or to residential treatment as usual using urn randomization balanced by biological sex (male vs female), race/ethnicity (White, Non- Hispanic vs Non-White, Hispanic), and days of substance use (1-45 vs 45+). Randomization will be done by the research staff using a randomization spreadsheet immediately at the end of the baseline assessment; condition assignments will then be immediately told to the family. Those assigned to the adapted PW condition will be scheduled for their first remote coaching session approximately 4 weeks prior to discharge (described below).

Protecting confidentiality. Steps taken to protect the confidentiality of participants are detailed in **Section D, “Possible Risks and Anticipated Benefits”** in the paragraphs focused on minimizing risk of loss of confidentiality.

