By using the GAIN at follow-ups, we will capture continuous data on the teen's use and high-risk behaviors following discharge. We will also include measures of parental communication and monitoring (Aim 4), as these outcomes are not included in the GAIN and parenting practices are a key factor associated with ASUD. PI [name] is a certified GAIN trainer and has experience analyzing GAIN data. Specific scales that we will analyze to address Aims 2 and 3 are described below.

Demographics. The GAIN Background section collects routine socio-demographic variables including age, sex, ethnicity, race, and grade in school. Items in other GAIN sections indicate the teen's history of substance use or mental health treatment utilization, data that will be used to control for additional treatment received.

Substance Use. The following GAIN items/scales and biological markers will address Aim 2 (substance outcomes).

Days of Use (Past 90 Days). A series of GAIN items evaluate days of substance use over the past 90 days. These items have shown excellent comparability to the well-validated Timeline Follow-Back Interview (TLFB). Like the TLFB, the GAIN assesses days of alcohol and drug use using a calendar with temporal cues (e.g., holidays, special events) to facilitate recall. We will analyze three variables, separately for alcohol, marijuana, and other drugs: total number of use days, total days abstinent, and latency to first use.

Substance Frequency Scale (SFS). The SFS scale averages the percent of days in the past 90 during which there was use of alcohol, marijuana, or heavy drugs; use to intoxication; and failure to perform activities due to use. This scale has good reliability ($\alpha = .85$) and predicts substance-related problems as well or better than biometric (e.g., urine) markers of use.

Biological markers. Biological markers will **only be used at the follow-up assessments (6, 12, and 24 weeks)**, since adolescents are not expected to have access to substances at the time of the baseline assessment (likely to be at least 1-2 days after admission). 8-panel urine screens that detect the presence of marijuana, cocaine, amphetamines, methamphetamines, MDMA, opiates, oxycodone, and benzodiazepines mailed to each family and administered to the teens by the parents will be used to provide a biological indicator of abstinence. Teens who present as acutely intoxicated based on researcher observations, parent-report, or adolescent-report will be rescheduled.

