discharge and ≥ 1 of 2 sessions post-discharge for $\geq 75\%$ of parents, and online usage patterns of 3+ PW logins, 2+ parent board logins, and 2+ hours logged in for $\geq 75\%$ of parents. Criteria for acceptability include withdrawal rates ($< 20\%$), satisfaction ratings ($\geq 80\%$ of CSQ items rated “agree” or “strongly agree”) and positive feedback from the exit interviews with parents and therapists. Criteria will be finalized based on parent and staff feedback in Phase 1.

Aims 2 - 4. The dependent variables (DVs) include substance use (Aim 2), related high-risk behaviors (Aim 3), and parental monitoring and communication (Aim 4, putative mediators). By nature of residential treatment, we expect teens’ level of substance use and risk behavior to start high at intake, drop off for the duration (~ 3.5 months) of treatment and then increase over the follow-up period. Trajectories that begin at baseline would be misleading, since all teens will have a sustained period of abstinence (with minimal variance). We therefore compare trajectories of use over the follow-up period, while controlling for baseline status as covariates.

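### Adjusting the Aims 2-4 models for treatment received during follow-up means the estimated PW effect need not equal the randomised (ITT) effect

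*Combined protocol and SAP*

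**What the plan says.** The Data Analysis Plan (Aims 2-4) specifies a separate mixed model for each dependent variable, with condition as predictor. The covariates are the baseline value of that variable, baseline differences between groups, and "any mental health or substance use treatment received over the follow-up period". No mixed model without the last covariate is specified, and the adjusted model is not labelled as supplementary.

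Other statements bear on this:

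- The opening paragraph of the Data Analysis Plan gives a general rule that "any additional treatment received will be controlled in subsequent analyses". In the same paragraph it says: "All 60 parents will be included in statistical analyses consistent with an intent-to-treat (ITT) model".
- Demographics, under Measures, describes the GAIN items on treatment history as "data that will be used to control for additional treatment received".
- Randomization says that allocation is made "using a randomization spreadsheet immediately at the end of the baseline assessment".
- An earlier paragraph of Aims 2-4 names baseline adjustment only: "We therefore compare trajectories of use over the follow-up period, while controlling for baseline status as covariates".
- The analysis starts with a simple comparison: "We will begin by comparing the DV scores (means of continuous DVs and percentages of categorical DVs) at each assessment". It names no covariates and is not designated as the effect estimate.
- Aims 2-4 makes the effect size of PW on each outcome, with its 95% CI, the main goal of these analyses. Sample Size, Power, and R01 then sizes the next trial from the effect size observed here, without saying which analysis supplies it.

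**The concern.** Treatment received after discharge is observed after randomisation, so the intervention can affect it. Hypothesis 2a expects PW to improve "substance use frequency, severity of substance use symptoms, rates of relapse, and biological markers". If relapse leads some adolescents back into treatment, an effective intervention would change the treatment covariate. Holding that covariate fixed then removes part of the effect. It also compares adolescents with the same treatment status across arms, who need no longer be comparable on severity.

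Analysing all 60 parents settles who is in the analysis set. It does not restore the randomised contrast once the model conditions on a consequence of randomisation. At stake are the effect size and CI for each outcome, and the sample size of the later trial if that effect size is carried forward.

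**Working it through.** **1. The plan's own figures.** For power 0.80, with two-sided alpha 0.05 and 1:1 allocation assumed, n per group = 2 × (1.96 + 0.8416)² / d² = 15.70 / d².

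- d = 0.3: 15.70 / 0.09 = 174.4, so 175 (plan: 175).
- d = 0.5: 15.70 / 0.25 = 62.8, so 63 (plan: 64; the t-test calculation gives 63.8, so 64).

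The figures reproduce. They do not test the concern, but they show how the effect size would be used.

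**2. When the two effects agree.** Score the outcome Y so that higher is better, with within-arm SD 1. Let T indicate treatment during follow-up, p₁ and p₀ the uptake under PW and usual treatment, and r the within-arm correlation of T with Y. In a linear model:

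adjusted coefficient = d − (r / SD_T) × (p₁ − p₀)

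This equals d only if p₁ = p₀ or r = 0. The plan secures neither. It adjusts because it expects treatment to matter, and Aims 2-4 itself expects use to drop during residential treatment.

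**3. Illustration with an uptake difference.** The documents give none of these inputs, so all are assumed: true d = 0.50, uptake 35% under usual treatment, and SD_T pooled within arm, for example √[(0.35 × 0.65 + 0.50 × 0.50) / 2] = 0.489.

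| Uptake, usual treatment vs PW | SD_T | r (±) | Shift = r × difference / SD_T | d, outcome-SD scale | d, residual-SD scale (÷ √(1 − r²)) |
|---|---|---|---|---|---|
| 35% vs 45% | 0.487 | 0.1 | 0.021 | 0.48 or 0.52 | 0.48 or 0.52 |
| 35% vs 50% | 0.489 | 0.2 | 0.061 | 0.44 or 0.56 | 0.45 or 0.57 |
| 35% vs 55% | 0.487 | 0.3 | 0.123 | 0.38 or 0.62 | 0.40 or 0.65 |

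The lower value arises when treated adolescents do better within arm (r positive). The higher value arises when treated adolescents are the more severe cases (r negative). The residual scale is the one behind partial eta squared.

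Unrounded, the middle row gives d = 0.439 or 0.561. The formula in step 1 then gives 15.70 / 0.439² ≈ 82 or 15.70 / 0.561² ≈ 50 per group, against 63.

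**4. Relapse path alone.** Suppose PW alters treatment only by altering the outcome, with T linear in Y. If T changes by c per unit of Y, then p₁ − p₀ = c·d and r / SD_T = c / SD_T². The coefficient is d(1 − c² / SD_T²) = d(1 − r²).

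- r of size 0.1, 0.2, 0.3: 0.495, 0.480, 0.455. The shift is toward zero and at most 0.045.
- Residual scale, d√(1 − r²): 0.497, 0.490, 0.477.

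**5. Repeated-measures check.** A simulation used three follow-ups, a random intercept (ICC 0.3, 0.5 and 0.7), a true effect of 0.50 SD, and treatment in each interval reacting to use (logit slope 0.5). The unadjusted coefficient was 0.50. The adjusted coefficient was:

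- 0.467 to 0.479 with an ever-treated indicator (r 0.21 to 0.26; the formula predicts 0.466 to 0.478);
- 0.478 to 0.489 with a per-interval indicator;
- 0.440 to 0.460 with the proportion of intervals treated, where r reaches about 0.34.

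With no reaction of treatment to use, adjusted and unadjusted coefficients agreed at 0.50.

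**6. Sampling error.** With 25 per arm, the 95% CI half-width at d = 0.5 is 1.96 × √(2/25 + 0.5²/100) = 0.563. With 30 per arm it is 0.514.

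**The case against.** The strongest reply concerns weight. Aims 2-4 are secondary in a pilot, the plan acknowledges that effect sizes are unstable in small samples, and every shift above is small against a half-width of 0.56. The wider range (0.38 to 0.62) needs an uptake difference of 10 to 20 points. Yet no PW component is described as aiming at treatment uptake, and answers on the parent board direct parents to PW modules. The path tied to the plan's hypothesis is relapse, and it moves d by at most 0.045 for r up to 0.3. Even there, that relapse leads to treatment is an assumption, and the path is most natural for the substance use outcomes of Aim 2. All of this stands, and it limits the severity.

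Three technical limits also stand. The figures are for continuous outcomes in linear models. For categorical outcomes in a logistic model, equal uptake does not guarantee equal coefficients. With equal uptake the coefficient is unchanged, but an effect size on the residual-SD scale still changes (0.50 / √0.91 = 0.524 at r = 0.3).

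The general rule on additional treatment gives no timing, and the Demographics sentence speaks of history. Only the covariate list in Aims 2-4 is explicit about follow-up. That list is nonetheless the only one given for the mixed models.

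Finally, the unadjusted comparison of means and percentages could be the source of the effect size for the next trial. The plan does not say so, nor that this comparison adjusts for baseline.

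**Conclusion.** The concern holds. The only mixed models specified for Aims 2-4 condition on a post-randomisation variable, so their condition coefficient need not equal the ITT effect that the plan says it follows.

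The size cannot be computed from the documents. It may be zero. On the stated assumptions it is at most 0.045 toward zero through relapse alone, and 0.02 to 0.12 in either direction if uptake differs by 10 to 20 points. Sampling error dominates in a trial with about 50 complete dyads. Unlike sampling error, this bias is not reflected in the CI and would carry over if the same model were used in the larger trial.

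This should be fixed, because the effect size is the stated goal of these analyses. It is not graver than that, because the aims are secondary and feasibility and acceptability also count in the decision to proceed.

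**What to change.** - For each outcome, define the main model as condition, time, the baseline value of the outcome and baseline covariates named in advance. This agrees with the plan's own statement about controlling for baseline status.
- Report mental health and substance use treatment during follow-up by arm, as an outcome.
- Keep the model adjusted for follow-up treatment as a labelled sensitivity analysis.
- State in Sample Size, Power, and R01 that the effect size and 95% CI carried forward come from the main model, with the CI width shown.
- Align the general rule in the Data Analysis Plan, and the Demographics sentence so far as it covers treatment after randomisation. Treatment history before randomisation can stay as a baseline covariate.

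The cost is wording only. No new data are needed and no planned analysis is lost. If outcome data have already been examined, the change should be dated and labelled as made after that point.
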